#### 1.7 Index Tests

The index tests will be stool FIT and urine VOCs.

#### 1.8 Reference Standard

The reference standard will be complete colonoscopy or CTC.

#### 1.9 Clinical data

Both FIT and urine VOC have potential to detect SBD but their diagnostic accuracy may be improved if used in combination; either in series (VOC in FIT negatives) or both in parallel.

#### Evidence of stool FIT in SBD detection

Our previous data and that of others have shown that stool FIT on its own has sensitivities of 80%, 53% and 86% for colon cancer, adenomatous polyps and inflammatory bowel disease respectively (2, 11, 13). Importantly, the alternative stool marker faecal calprotectin (FCP) offers no added advantage for the added cost (2, 11). The sensitivity of FCP for colon cancer is lower at 68% (vs 80%) and 43% (vs 53%) for adenomatous polyps compared to FIT but comparable for diagnosis of inflammatory bowel disease (for which it is intended) (3). This has meant that NICE has not recommended FCP for diagnosis of SBD

IRAS 282247\_RECEDE protocol\_v2.2\_11.02.2022 Page **15** of **50** 

except inflammatory bowel disease. Note that blood or stool based genomic markers e.g. mSEPTIN 9, Cologuard (methylated DNA markers) whilst specific for CRC perform less well to identify colonic polyps (sensitivity 60% with specificity of 46%) (14). Moreover, these markers cannot identify other SBD such as inflammatory bowel disease. Their high cost (15) makes it prohibitive for routine use with almost comparable cost to that of a colonoscopy. Conversely, urine VOCs on their own can detect SBD with sensitivities for colon cancer, adenomatous polyps and inflammatory bowel disease at 80%, 92% and 86% respectively (6, 16),(17). Of further note, concordance between FIT and urine VOC is low to moderate indicating a potential synergistic effect when combining results from the two tests.

FIT (£18 per test) is recognised to be superior to the guaiac faecal occult blood test for detecting CRC due its ability to detect human haemoglobin (18). There is good evidence for its use within the screening population. In those with symptoms, there has been increasing evidence supporting its use in primary and secondary care. However, significant limitations as outlined earlier are the number of missed CRC cases, and lack of sensitivity and specificity to detect pre-malignant lesions (polyps) (6, 7, and 12). Thus, it is apparent that FIT on its own is not likely to be sufficient to detect SBD, but rather a second complementary test is required to improve SBD detection.

Existing evidence suggests that FIT on its own can miss up to 10% of CRC (applying threshold recommended by NICE), but adding urine VOC testing can reduce this to 3% (similar to colonoscopy) (6).

Studies to date in those with lower gastrointestinal symptoms utilising FIT for detection of CRC provides sensitivities ranging from 80-92%. Some of these studies included testing in primary care and others in secondary care. A systematic review undertaken in 2017(7) and subsequently updated by our group in 2019(19), of studies in 6755 patients with lower gastrointestinal symptoms concluded that FIT (at a threshold of 20µgHb/g faeces) would achieve a 90% sensitivity (95% confidence interval, CI: 87 to 92) and 86% specificity (95% CI: 83 to 90) for CRC detection – Figure 2. The meta-analysis reviewed studies applying varying thresholds from 7 to 97  $\mu$ g Hb/g faeces as well as evaluated different diagnostic kits used to measure FIT.

**Figure 2** Forest plot of sensitivity and specificity of FIT for detection of CRC in 6755 symptomatic participants. The pooled sensitivity was 0.90 (95%CI: 0.87 to 0.92) and specificity 0.86 (95% CI: 0.83 to 0.90) represented by the red dashed line.

IRAS 282247\_RECEDE protocol\_v2.2\_11.02.2022 Page 16 of 50

#### Evidence of urine VOC in SBD detection

VOCs are organic molecules that have a low boiling point, which results in a large number of these molecules evaporating from a liquid (or even sublimating from a solid form) to the surrounding air. Large numbers of VOCs are generated from natural or artificial sources. The detection of VOCs is a mature technology and has been used successfully in a range of applications from security, food and drug quality/freshness and pollution monitoring (14).

VOCs vary in abundance and mobility in health and disease. Measurement from biological samples provide an indirect reflection of cellular/tissue health based on the metabolic output profile measured as a 'chemical fingerprint'. They are as equally informative as genetic tests in terms of probability of having a disease and able to provide this information in real time. VOCs were first reported in the 1970s by Nobel Laureate Linus Pauling who detected inflammatory conditions in urine samples. (21) Urine VOC analysis has had resurgence of interest in the last decade largely due to its ease in measurement (on the spot collection) and advancement in sensor technology, which is now available at relatively low cost, £25 per test. VOCs have a strong translational component from *in vitro* application to measure cellular differentiation (22) to clinical diagnosis of respiratory, gastrointestinal diseases, wound infection and cancers (including non-gastrointestinal) (23, 24).

Unlike faeces, urine collection for VOC measurement can be collected at time of point of care testing. Subsequently, it can be sent to a central laboratory for analysis (as with FIT) allowing contemporaneous results to guide clinicians with decision making. Thus, it lends itself as an ideal clinical test.

VOCs detected in urine of those with SBD reflect metabolic processes either directly from the tumour/inflamed mucosa, from the distinct microbiome dysbiosis commonly associated with neoplasia and IBD (17, 25, 26) or more likely, from an interaction between both entities.

We and others have studied VOC detection for CRC using different modalities – faeces, urine and breath (16, 27-29). The sensitivities range from 80-92% (95% CI: 63 to 94). More recently our group has also shown utility of urine VOC in CRC detection in those within the BCSP population (30). Our group has optimised methods for VOC detection in urine from sample collection, storage and stability as well as specific algorithm for analysis (6, 31, 32). This both allows for VOC analysis to be introduced into conventional secondary care laboratory setting and for its diagnostic utility to be optimised. We have already identified four potential key chemicals that are associated with CRC detection (cyclooctatetraene, propanediamine, methylbenzoic acid and isothiocyanate) (33) that contributes to 20 discriminant features providing a score that can be quantified and threshold adjusted accordingly – see Appendix A Table 1.

#### Dual Testing

Our further recent study has shown that dual testing (stool FIT followed by urine VOCs in the FIT negatives) improves the detection of colorectal cancer from 80% (95% CI: 0.63 to 0.93) to 97% (95% CI: 0.90 to 1.0) (6). Stool FIT detects the presence of human haemoglobin moiety thus in conditions where there is no overt bleeding (e.g. diminutive adenomatous polyps, microscopic colitis) the test if used on its own becomes less sensitive. Volatile organic compounds (VOCs) on the other hand are compounds produced by interaction of the host in the presence of illness and are therefore *disease* specific. These compounds are of low molecular weights and result from cellular interaction with the gut microbiome in the presence of disease.

If used in combination, the diagnostic accuracy of these tests (stool FIT and urine VOC) should improve the detection of SBD as shown with colon cancer and adenomatous polyps (Figure 3). Based on our previous study, 37% of those with SBD test FIT negative. In this preliminary study, of the 7 individuals with cancers missed by FIT alone (FIT negative CRC), 6 of them were subsequently identified when urine VOCs were added. Existing studies have demonstrated the utility of urine VOC to detect not just colon

IRAS 282247\_RECEDE protocol\_v2.2\_11.02.2022 Page **17** of **50** 

cancer or inflammatory bowel disease but other gastrointestinal diseases including coeliac disease and bile acid diarrhoea, but be negative in benign conditions such as irritable bowel syndrome (IBS) (34, 35). The importance of this is the premise that the triage tests (urine volatile markers) can distinguish SBD from those without SBD (e.g. IBS). NICE recommends that IBS can safely be managed in primary care without recourse to referral to secondary care for invasive and expensive investigations (36).

**Figure 3:** Two plots showing the stages of the FIT/VOC two-stage test. The left-hand plot shows the distribution of FIT measurements for CRC-positive and CRC-negative participants. The dotted line shows the threshold for the first stage test. Participants above this threshold are classed as positive for the test, while participants below this threshold go on to the second stage of VOC screening, shown in the right-hand plot. For participants who are screened using VOCs, the distribution of predicted probabilities of CRC are significantly reduced as shown in the right-hand plot, with the decision threshold again shown by a dotted line. Participants above the line are positive for the test, while participants below the line are negative (6).

#### Evidence of urine VOC in other diseases

Urine VOCs on their own can detect SBD with sensitivities for colon cancer, adenomatous polyps and inflammatory bowel disease at 80%, 92% and 86% respectively (6, 17, 18).

Our previous work has identified key urinary metabolites in 'inflammatory' gastrointestinal diseases other than CRC. Table 2 below demonstrates key urinary VOCs that are identified in specific conditions including relative abundance (19). The importance of these findings are that it highlights that the technique applied for urinary VOC detection is feasible in separating CRC including that of pre-cancerous lesions such as adenomas from other overlap gastrointestinal conditions.

**Table 2** Specific compounds identified in urine by relative incidence in different disease groups – CRC, colorectal polyps (adenoma), inflammatory bowel disease, irritable bowel syndrome, coeliac disease and healthy volunteers. Key volatile metabolites can be identified in urine of those with CRC and are sufficiently diverse from other disease groups including pre-cancerous lesions.

Colorectal Cancer		
High Incidence Low Incidence		

1,3,5,7-Cyclooctatetraene	Oxime-, methoxy-phenyl-		
	1,3-Propanediamine		
Irritable Bo	Irritable Bowel Syndrome		
Isothiocyanate			
1,3,5,7-Cyclooctatetraene			
Phenol, 2,4-bis(1,1-dimethylethyl)-			
Inflammator	y Bowel Disease		
1,3-Propanediamine	Phenol, 2,4-bis(1,1-dimethylethyl)-		
4-Heptanone	1,3,5,7-Cyclooctatetraene		
	2-Pentanone		
Healthy	Volunteers		
Oxime-, methoxy-phenyl-	Ethanone, 1,1'-(1,4-phenylene)bis		
	1,3,5,7-Cyclooctatetraene		
	1,3-Propanediamine		
Colorectal Po	lyps (Adenomas)		
	Phenol, 2,4-bis(1,1-dimethylethyl)-		
	Oxime-, methoxy-phenyl-		
	1,3,5,7-Cyclooctatetraene		
	4-Heptanone		
	Acetone		
Coelia	c Disease		
1,3-Propanediamine	Phenol, 2,4-bis(1,1-dimethylethyl)-		
Oxime-, methoxy-phenyl-	2-Pentanone		
1,3,5,7-Cyclooctatetraene			

#### 2 RATIONALE

We hypothesise that the dual testing with stool FIT and urine VOC tests is more sensitive than stool FIT alone in detecting SBD using colonoscopy (complete examination) or CTC as the reference standard.

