#### STUDY PROTOCOL

**RECEDE study (Reducing Colonoscopies in those without bowEl DiseasE)** 

#### **1** SUMMARY OF RESEARCH

#### 1.1 Lay Summary

Investigating people with bowel symptoms uses a test that detects traces of blood in the stools, the FIT test. There are many possible reasons for positive tests. A few people have cancer. However, most participants with symptoms don't have any serious bowel disease but have benign problems such as piles or irritable bowel syndrome (IBS). It is very difficult to diagnose on symptoms alone, those participants who have serious bowel disease and those who do not.

After a positive test, people are invited for colonoscopy– a sort of articulated tube that is passed up the bowel, or a computed tomography colonography (CTC) – a radiological technique used to image the large bowel. Most people invited for colonoscopy or CTC don't have cancer. Only about 5% of those with positive FIT tests have cancer. About 25% have other serious bowel diseases (pre-cancerous polyps or inflammatory bowel disease), but most have nothing serious wrong at all. So they have the inconvenience and discomfort of having a CTC or colonoscopy but don't get any benefit from it.

We want to try adding another test, the volatile organic compound (VOC) test, to see if we can separate those with positive FIT tests who do have something serious, from those who don't. The VOC test uses a urine sample. Using both tests might also be better for detecting cancer and other serious bowel diseases. FIT alone misses about 20%.

So we think that using both tests might not only be better for detecting cancer, but also might mean that a lot of people will avoid having to have an invasive colonoscopy or CTC.

We will recruit 1,915 participants with bowel symptoms from NHS trusts in the UK. They will provide stool samples for FIT and urine for VOC analysis. They will have colonoscopy or CTC to get a definite diagnosis. Then we will look at their FIT and VOC test results to see if in future, people with both tests negative don't need invasive colon investigations.

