#### Primary outcome

Primary outcome will be diagnostic accuracy for sensitivity, specificity, NPV and PPV of stool FIT plus urine VOC compared to stool FIT alone in the detection of SBD.

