#### 8.2.2 Primary outcome analysis

The primary outcome is diagnostic accuracy - sensitivity, specificity, NPV and PPV of the dual index test, FIT and VOC. A FIT result that is >10 µgHb/g faeces OR a VOC result with predicted probability >0.63 implies that the participant is defined as having SBD and need to be referred for colonoscopy. We will report 2x2 tables of test accuracy of the dual test by the reference standard (final report from the CTC or colonoscopy examination and confirmatory histology report of SBD which is either colon cancer, colorectal adenomas or inflammatory bowel disease), alongside summary measures of sensitivity, specificity, NPV and PPV, and their 95% confidence intervals. Confidence intervals for sensitivity and specificity estimates that are very close to 1.0 will be according to the Zhou-Li method and the intervals for NPV and PPV estimates that are very close to 1.0 will be according to the Bayesian method (38). These test accuracy estimates will be used in the economic model.

We will analyse the combined FIT+VOC test results as both parallel (results from both tests are interpreted in combination) and serial testing (VOC performed only if FIT negative, i.e. <10  $\mu$ gHb/g faeces). The "or" rule will be considered in the interpretation of both parallel and serial tests where the diagnosis is positive when either test is positive (FIT >10  $\mu$ gHb/g faeces and/or VOC predicted probability >0.63), and negative when both are negative (FIT <10  $\mu$ gHb/g faeces and VOC predicted probability <0.63). In the serial test, if the FIT is positive (FIT >10  $\mu$ gHb/g faeces) then the diagnosis is positive. Otherwise, use the result from VOC and if it is positive (VOC predicted probability >0.63) then the diagnosis is positive. If the VOC result is also negative then the diagnosis is negative. Mathematically, both methods would give the same diagnostic results but would make a difference in the economic model.

A 2x2 table of test accuracy for each individual index test by the reference test will also be presented. Sensitivity, specificity, PPV and NPV will also be presented with their 95% confidence intervals for FIT only and VOC only. Participants with missing data for either of the index tests (FIT or VOC) or the reference standard (colonoscopy) will be excluded from this analysis.

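### Under the primary either-positive rule, higher sensitivity than FIT alone is built in and does not show that VOC adds value; Section 8.2.2 defines no dual-versus-FIT contrast although that contrast is the aim

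*Protocol*

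**What the plan says.** The hypothesis in Section 2 (Rationale) is: "We hypothesise that the dual testing with stool FIT and urine VOC tests is more sensitive than stool FIT alone in detecting SBD". The study aim in the Study Summary, Section 1.2 and Section 2.1 is likewise dual testing compared with FIT alone. The primary outcome in Section 1.2 is the accuracy of "stool FIT plus urine VOC compared to stool FIT alone in the detection of SBD".

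Section 8.2.2 words the primary outcome without a comparator: "The primary outcome is diagnostic accuracy - sensitivity, specificity, NPV and PPV of the dual index test, FIT and VOC". It fixes one rule for parallel and serial testing, "where the diagnosis is positive when either test is positive", and accepts that the order of testing does not change the classification: "Mathematically, both methods would give the same diagnostic results but would make a difference in the economic model". For the single tests it adds: "Sensitivity, specificity, PPV and NPV will also be presented with their 95% confidence intervals for FIT only and VOC only".

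The Lay Summary (Section 1.1) gives VOC a different job, "to see if we can separate those with positive FIT tests who do have something serious", as distinct from those who do not.

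Section 8.2.3 adds secondary analyses. These are threshold selection at 97% sensitivity for each test and for combinations, FIT cut-offs from 7 to 120, and a rule requiring both tests to be positive.

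**The concern.** Adding a second test under an either-positive rule can only move people from negative to positive. A rise in sensitivity over FIT at the same cut-off is therefore a property of the rule, and it comes with a fall in specificity, or at best no change. A hypothesis that speaks only of sensitivity cannot tell a useful VOC test from a random one.

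Three things follow.

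- The contrast that the protocol names as its aim has no defined estimand in the primary analysis section.
- The direction of the avoided-procedures result depends on the comparator. The dual test may spare many procedures against investigating everyone, but under the primary rule it can only add to the number referred by FIT alone at the same cut-off.
- The Lay Summary describes VOC as sorting FIT-positives. Under the primary rule VOC never changes a FIT-positive result.

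**Working it through.** **Plan's own figure.** Section 8.1 asks for 200 SBD cases at 19% prevalence and 55% return of both samples. 200 / 0.19 = 1,053 evaluable and 1,053 / 0.55 = 1,915, as stated. This sizes one proportion (sensitivity 0.97, 95% CI width 0.05), not a comparison.

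**Algebra.** At a common FIT cut-off:

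- Se(dual) = Se(FIT) + (1 − Se(FIT)) × P(VOC+ | FIT−, SBD)
- 1 − Sp(dual) = (1 − Sp(FIT)) + Sp(FIT) × P(VOC+ | FIT−, no SBD)

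Both added terms are zero or positive, so sensitivity and referrals cannot fall and specificity cannot rise.

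**Inputs for an illustration.** 200 with SBD and 853 without (Section 8.1). FIT sensitivity for SBD is 0.63, from the 37% of SBD that is FIT-negative (Section 1.9, Dual Testing). FIT specificity 0.93 and VOC sensitivity and specificity 0.63 each come from Appendix D. These last three are colorectal cancer figures, applied to SBD as an assumption.

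**Results with the tests independent given disease status**

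| | Sensitivity | Specificity | SBD referred | Non-SBD referred | Total |
|---|---|---|---|---|---|
| FIT alone | 0.63 | 0.93 | 126 | 59.7 | 186 |
| Dual | 0.63 + 0.37 × 0.63 = 0.863 | 0.93 × 0.63 = 0.586 | 172.6 | 353.2 | 526 |

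**Range over all possible dependence.** Dual sensitivity lies between 0.63 and 1.00, and specificity between 0.56 and 0.63.

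- Fewest referrals: 200 × 0.63 + 853 × 0.37 = 442
- Most referrals: 200 × 1.00 + 853 × 0.44 = 575

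That is about 2.4 to 3.1 times the 186 referred by FIT alone.

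**Comparator for avoided procedures.** Against investigating everyone, about 500 people without SBD are spared under the dual test (853 × 0.586) and about 793 under FIT alone (853 × 0.93). Against FIT alone, the dual test therefore adds about 293 procedures in people without SBD.

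**An uninformative VOC.** Let VOC be positive at random in 37% of everyone. Sensitivity still rises, from 0.63 to 0.63 + 0.37 × 0.37 = 0.77. What changes is the price:

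- Informative VOC (0.63/0.63): extra non-SBD per extra SBD = (353.2 − 59.7) / (172.6 − 126) = 293.5 / 46.6 = 6.3
- Random VOC: 293.5 / (74 × 0.37) = 293.5 / 27.4 = 10.7

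For a random VOC this ratio is the same at any positivity rate, because it equals 793.3 / 74. It is therefore a natural benchmark.

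**A paired test of sensitivity alone would not repair this.** All discordance runs one way, so six FIT-negative/VOC-positive SBD cases give an exact McNemar p of 2 × 0.5⁶ = 0.031. With 74 FIT-negative SBD cases, a VOC positive at random in 10% reaches six with probability 0.76.

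**Precision.** The gain is a single proportion, b = 0.37 × 0.63 = 0.2331.

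- Paired 95% half-width: 1.96 × √(0.2331 × 0.7669 / 200) = 0.059
- Treated as independent: 1.96 × √(0.63 × 0.37 / 200 + 0.863 × 0.137 / 200) = 0.082

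**The case against.** Four stronger readings are tempting, and the protocol does not support them.

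- *The hypothesis cannot fail or cannot be tested.* Strict superiority fails if VOC finds no FIT-negative SBD, and the size of the gain is a real quantity. Specificity, PPV and NPV are reported in the same analysis, so a worthless VOC would show up as lost specificity. The accurate statement is that the direction cannot be reversed.
- *VOC cannot reduce procedures relative to FIT.* This holds for the primary rule at a common FIT cut-off. The both-positive rule in Section 8.2.3, or an either-positive rule with FIT above 10, can refer fewer than FIT at 10.
- *No paired comparison will be made.* Section 2.1 lists comparative accuracy as an objective, a full SAP is promised, and that SAP is not available here. Section 8.2.2 excludes anyone lacking either index test or the reference standard. Because the rule is nested, the paired counts can be recovered from its 2×2 tables.
- *The trial will claim a significant gain.* No significance test of dual against FIT appears in the protocol.

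Section 8.2.3 also already selects thresholds for FIT alone and for combinations at the same 97% sensitivity. This is an informative comparison, though the section does not state it as one and itself describes the resulting accuracy as overestimated.

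On avoided procedures, Section 8.1 does suggest investigating everyone as the comparator. However, Sections 2.1 (Economics) and 8.3 compare dual testing with FIT alone, so the comparator is not fixed.

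The illustration is also open to challenge. Besides borrowing cancer figures, it takes FIT accuracy from a study whose threshold was derived from its own data (Section 1.2). Appendix E Table 3 shows 135 of 612 positive at 10 or above (22%), or about 232 of 1,053 rather than 186. The size therefore moves; the direction does not.

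**Conclusion.** The point holds for the primary rule at a common FIT cut-off. There, higher sensitivity is met in direction by any second test, and it is no evidence that VOC adds value. This part is algebra and needs no assumption.

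Two inconsistencies also stand on the text alone. The primary outcome is comparative in Section 1.2 and dual-only in Section 8.2.2. The Lay Summary's purpose of sorting FIT-positives cannot be served by the primary rule.

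The size (about 186 referrals rising to about 526, range 442 to 575) is an illustration. It rests on cancer specificities and a cancer VOC sensitivity applied to SBD, and the central value also rests on conditional independence. The design and data collection are sound; the weakness is in how the headline comparison is defined and could be read.

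**What to change.** 1. Reconcile the primary outcome in Sections 1.2 and 8.2.2, so that both state whether the comparison with FIT alone is primary.
2. In Section 8.2.2, report the paired gain in sensitivity together with the paired loss in specificity, each with a paired 95% CI. These are the FIT-negative/VOC-positive proportions in SBD and in non-SBD. Add the extra non-SBD referrals per extra SBD case found.
3. Restate the Section 2 hypothesis as that trade-off. Use the 97%-sensitivity thresholds already planned in Section 8.2.3 to compare FIT alone with the dual test explicitly, keeping that section's caveat on optimism.
4. Report colonoscopies and CTCs avoided in two separate counts: against investigating everyone, and against FIT alone.
5. Reconcile the Lay Summary wording with the primary rule, or report VOC accuracy within FIT-positives.

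The cost is some rewording and a few more tables from data already collected, with no extra participants. The downside for the sponsor is a less favourable headline against FIT alone.
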